## **Arms and Interventions**

Arms	Assigned Interventions	
Experimental: EXO-1 Participants (n=10) in this group will receive standard therapy and exosomes of the first type.	Procedure/Surgery: EXO 1 inhalation Twice a day during 10 days inhalation of 3 ml special solution contained 0.5-2x10^10 of nanoparticles (exosomes) of the first type.	
Experimental: EXO-2 Participants (n=10) in this group will receive standard therapy and exosomes of the second type.	Procedure/Surgery: EXO 2 inhalation Twice a day during 10 days inhalation of 3 ml special solution contained 0.5-2x10^10 of nanoparticles (exosomes) of the second type.	
Placebo Comparator: Placebo Participants (n=10) in this group will receive standard therapy and inhalation placebo solution.	Procedure/Surgery: Placebo inhalation Twice a day during 10 days inhalation of 3 ml special solution free of nanoparticles (exosomes).	

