#### Research methods and STATISTICAL CONSIDERATIONS

Title	Purpose	Method	Frequency	Statistics
Number of	Safety	Collection of	After each	Numeric data, calculated
participants with minor and serious side effects	assessment of the procedure.	information about unwanted reactions to inhalation, for example, 1) temperature increase, 2) allergic reaction in the form of swelling Quincke, rash, seizures, etc.; 3) bronchospasm for inhalation	procedure	as a percent from whole patients in the group.
Biochemistry of blood	Evaluation of procedure efficiency	C-reactive protein, LDH	At the beginning of inhalation (day 1) and on next day of last inhalation (day 11)	The difference in each group between baseline and day 11 will be measured by T-test. The data will be presented as a Mean with full range (minmax). The difference will be calculated as Mean

				difference with Standard Deviation (SD)
Time to Clinical Recovery (TTCR)	Evaluation of procedure efficiency	Calculation of days in hospital	Once at the end of trial	The data will be presented as a Mean with Standard Deviation (SD)
SpO2 Concentration Changes	Evaluation of procedure efficiency	The concentration of SpO2 by Pulse oximetry device during procedures and compared to placebo.	Before and after each inhalation (total 4 measures per day). 10 days.	The intraday data (4 measures per day) will be calculated as a Median by day. The Median by day data (10 measures) will be processed by T-test intragroup and between groups. The data in tables will be presented as a Median (Me) with 25-75 quartile range.

The results will be statistically processed using parametric and non-parametric statistics methods using STATA version 9.0, Statistica for Windows version 6.0 and MS Office Excel 2007. Changes from the start of therapy and after will be compared using the T-test, comparing data between the main group and the control group using non-parametric method box-plot (data are presented in Me - median format with an indication of 25% (q1) and 75% (q3) quartile.

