## STATISTICAL CONSIDERATIONS

This study will enroll patients with PCR confirmed COVID according inclusion criteria.

The trial has three groups, each with 10 subjects (n=30). All eligible study subjects will be randomized, double-blinded, to either the two treatment groups or placebo group. Two main groups will be provided with exosomes in a specially provided solution, the third group (control) will receive the same solution without exosomes. Due to exosomes are nanoparticles and requires special methods and devices to be detected the hospital staff and patients have no way to check which group receives exosomes.

This is interventional, prospective, randomized double-blinded with a control group study.

The primary outcomes will be assessed at discharge of the clinic and 1 month after. Duration of study participation will be 1 months from the time of discharge from the clinic.

It is estimated that up to 2-3 research participants will be enrolled each week and that approximately 4 weeks of accrual will be necessary to enroll 10 participants.

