#### **Demographics and Baseline Characteristics**

Demographics and baseline characteristics will be summarized for all research participants. Characteristics to be examined include age, sex. The results will be statistically processed using parametric and non-parametric statistics methods using STATA version 9.0, Statistica for Windows version 6.0 and MS Office Excel 2007. Changes from the start of therapy and after will be compared using the T-test, comparing data between the main group and the control group using non-parametric method, box-plot.

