## **EXPECTED RESULTS**

It is assumed that the inhalation method of injection of exosomes will speed up the rehabilitation of patients, reduce the volume of pulmonary tissue lesions and reduce the time of stay of patients in hospital conditions.

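### CRP and LDH are efficacy measures, but the only test named for them is within each arm; the comparison with placebo is left to a box-plot

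*Combined protocol and SAP*

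**What the plan says.** The table in Research methods and STATISTICAL CONSIDERATIONS gives blood biochemistry (CRP and LDH, days 1 and 11) an efficacy purpose. The only test in that row is within arm: "The difference in each group between baseline and day 11 will be measured by T-test". The rest of the row is descriptive: mean, range, mean difference and SD.

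The paragraph that closes the section gives the t-test to changes from the start of therapy. It handles exosomes against placebo by "comparing data between the main group and the control group using non-parametric method box-plot", shown as median and quartiles. Demographics and Baseline Characteristics repeats this: "comparing data between the main group and the control group using non-parametric method, box-plot".

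Two other rows help in reading this one:

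- SpO2 is the only row with a named between-group test: "The Median by day data (10 measures) will be processed by T-test intragroup and between groups".
- Time to Clinical Recovery (TTCR), measured as days in hospital and also an efficacy measure, has no test: "The data will be presented as a Mean with Standard Deviation (SD". Yet EXPECTED RESULTS anticipates that exosomes will "reduce the time of stay of patients in hospital conditions".

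Arms and Interventions gives standard therapy to all three arms. Placebo participants "in this group will receive standard therapy and inhalation placebo solution".

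**The concern.** Patients are randomized to placebo so that an exosome effect can be separated from recovery under standard therapy. A baseline-to-day-11 test inside one arm cannot do that. It responds equally to the product, to standard therapy, to natural recovery and to regression to the mean. A box-plot does not fill the gap, because it yields no estimate, interval or p-value. If a rank test was meant, the plan neither names it nor says what is compared with what. The text speaks of one main group although there are two exosome arms.

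The aim includes efficacy. Followed as written, the plan names no test of exosomes against placebo for either marker. The natural temptation is then to read a significant fall on exosomes and a non-significant one on placebo as evidence of benefit.

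**Working it through.** **What the plan supplies.** Three arms of 10 give 3 × 10 = 30, which matches the stated total. No alpha, power, effect size or SD stands behind that number, and no CRP or LDH change is given. There is therefore no planned power figure to reproduce, and what follows is an illustration.

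**Assumptions (not in the documents).** Two-sided 5%; normal changes with equal SD in all arms; one marker; a common mean recovery of *d* SDs of the change in every arm, with *d* = 0.3, 0.5, 0.7, 1.0 or 1.5.

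**Step 1: within-arm test.** The paired t-test with n = 10 has 9 degrees of freedom and noncentrality *d*√10. Let *p* be its probability of significance.

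**Step 2: no exosome effect.** The arms are independent, so:

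- a given exosome arm is significant and placebo is not with probability *p*(1 − *p*);
- at least one of the two exosome arms is significant and placebo is not with probability (1 − *p*)[1 − (1 − *p*)²].

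For example, at *d* = 0.5, *p* = 0.293. The first is 0.293 × 0.707 = 0.207, and the second is 0.707 × (1 − 0.707²) = 0.354.

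**Step 3: a real effect in one exosome arm.** Add a true extra change of 1.325 SD, the size a two-sample t-test at 10 versus 10 detects with 80% power. The pattern for that arm then has probability *p*(*d* + 1.325) × [1 − *p*(*d*)].

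| *d* (SD of change) | *p* within arm | No effect: given arm | No effect: at least one arm | Real effect: that arm |
|---|---|---|---|---|
| 0.3 | 0.136 | 0.118 | 0.219 | 0.859 |
| 0.5 | 0.293 | 0.207 | 0.354 | 0.707 |
| 0.7 | 0.506 | 0.250 | 0.373 | 0.494 |
| 1.0 | 0.803 | 0.158 | 0.189 | 0.198 |
| 1.5 | 0.987 | 0.013 | 0.013 | 0.013 |

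Simulation with 200,000 trials per value of *d* agrees with the no-effect columns to within 0.001; the real-effect column is from such a simulation.

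**Step 4: the between-arm comparison.** In the same simulated trials, the two-sample t-test of the change had an error rate of 0.050 to 0.051 per arm. For at least one of two exosome arms sharing the placebo arm it was 0.090 to 0.092. Recovery size made no difference. Its power against 1.325 SD was 0.80 throughout.

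**Step 5: reading the table.** With no exosome effect, the within-arm pattern exceeds the between-arm error at the first four recovery sizes and falls below it at 1.5 SD. With a real effect, the chance of seeing the pattern drops from 86% to 1% as recovery grows, because placebo becomes significant too. How often the pattern appears depends on how strongly everyone recovers, so it does not isolate the exosome effect.

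**The case against.** The best defence is that the comparison is underspecified rather than absent. The closing paragraph announces a non-parametric comparison with control that is not limited to one row, and it may be a loosely worded reference to a rank test displayed by box-plots. That reading is possible, and the documents cannot settle it. Even so, the test, the contrasts and the estimate would still have to be stated. The one test the CRP/LDH row does name answers a different question.

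A second objection is that the percentages describe a rule the plan never adopts. This stands. No decision rule is written, the result depends heavily on an unknown recovery size, and misreading is a risk rather than a certainty. The figures illustrate why the reasoning is unsound. They are not error rates of this trial.

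Third, the consequence is limited. This is a Phase 1/2 trial, and CRP and LDH are not identified as primary. STATISTICAL CONSIDERATIONS places primary outcomes elsewhere in time: "The primary outcomes will be assessed at discharge of the clinic and 1 month after". Both values are collected in all arms, so a proper comparison remains possible. This caps the severity but does not remove the defect.

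Finally, TTCR has a separate gap, since it has no test at all. None of the arithmetic applies to it, and it adds no weight here.

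**Conclusion.** The concern holds and should be fixed. For two markers declared as efficacy measures, the plan states a method that cannot isolate an exosome effect, and it names no usable test against placebo.

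Under the stated assumptions and with no exosome effect, the pattern of significance on exosomes but not on placebo arises in 1% to 25% of trials for a given arm, against 5% for a between-arm test. For at least one arm it is 1% to 37%, against 9%. The documents do not say where in those ranges this trial lies. The finding itself rests on the text and not on these figures. It limits the efficacy conclusions from CRP and LDH and leaves the safety data untouched.

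**What to change.** 1. Specify the CRP and LDH efficacy analysis as EXO-1 versus placebo and EXO-2 versus placebo, each with an estimate and 95% confidence interval. The day-11 value adjusted for day 1 is one option; a rank or permutation test on the change is another. Any prespecified between-arm method cures the defect.
2. If the box-plot wording meant a rank test, name it and its contrasts.
3. Keep the within-arm t-tests and box-plots as description.
4. Label the results exploratory or state how multiplicity is handled. Two contrasts on two markers make four tests.
5. In the same revision, say how TTCR is compared between arms, or that it is descriptive only.
6. Date the change relative to unblinding. Masking is stated only for participants and care providers, so the useful reference is first access to outcome data by arm. Study Design lists enrolment as actual, so label the change post hoc if it comes later.

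**Cost.** No new data are needed, because day-1 and day-11 values are already planned. Precision will be low. For an unadjusted two-sample t-test of the change, the 95% interval half-width is t(0.975, 18) × √(2/10) = 0.94 SD of change. About 1.32 SD is needed for 80% power at two-sided 5%, or 1.48 SD if alpha is split to 2.5% for each of the two contrasts. Baseline adjustment may help, but by how much depends on a correlation and SDs that the documents do not give. Results may look less favourable than the within-arm tests.

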## **Eligibility**

Minimum Age: 18 Years

Maximum 65 Years

Age:

Sex: All

Gender No

Based:

Accepts No Healthy

Volunteers:

Criteria: Inclusion Criteria:

- Ability to understand the study objectives and risks and provide signed and dated informed consent;
- Confirmed COVID-19 infection (by PCR or antibody test);
- Pneumonia requiring hospitalization, and oxygen saturation of <94% indoors or a need for auxiliary oxygen. The confirmed volume of lung damage by CT: not less than 30% and not more than 80%;
- · ability to proceed with inhalation by self;

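### CRP, LDH and SpO2 have no rule for patients who leave, are transferred or die before day 11, so t-tests on the available values risk outcome-related bias of unknown size and direction

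*Combined protocol and SAP*

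**What the plan says.** The outcome table under Research methods and STATISTICAL CONSIDERATIONS gives CRP and LDH two sampling times: "At the beginning of inhalation (day 1) and on next day of last inhalation (day 11"). The analysis is within group: "The difference in each group between baseline and day 11 will be measured by T-test", reported as a mean difference with SD. Between-group comparison is described below the table only as a non-parametric box-plot with medians and quartiles.

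SpO2 is measured as follows: "Before and after each inhalation (total 4 measures per day). 10 days". Each day's readings become one median, and "The Median by day data (10 measures) will be processed by T-test intragroup and between groups".

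Arms and Interventions sets the same course for every arm: "Twice a day during 10 days inhalation of 3 ml special solution". STATISTICAL CONSIDERATIONS gives the size: "The trial has three groups, each with 10 subjects (n=30"). It places assessment of the primary outcomes at discharge and one month later, and describes no visit on day 11 for a patient already discharged.

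Days in hospital is itself an efficacy outcome, and EXPECTED RESULTS says that treatment should "reduce the time of stay of patients in hospital conditions". The documents contain no discharge criterion, minimum stay, efficacy analysis set, missing-data rule, or statement on how death or transfer is handled.

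**The concern.** CRP and LDH have no value between day 1 and the end of treatment. A patient without the final sample therefore contributes no change at all. If the best recoverers go home first, their changes are missing and the remaining mean understates improvement. If the sickest die or are moved elsewhere, the remaining mean overstates it. Early departure is part of the hoped-for effect, so the loss may also differ between arms.

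Two details add to this. The day after the last inhalation is day 11 only for someone who inhales for the full 10 days; for anyone who stops earlier, the plan names two different dates and does not choose between them. And because SpO2 is tied to inhalations, a patient who stops inhaling has no further scheduled SpO2 reading, even if still in hospital.

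At stake is whether the reported changes in CRP, LDH and SpO2 describe all patients randomised or only those still under treatment at the end.

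**Working it through.** **Inputs from the documents.** Three arms of 10 (3 × 10 = 30, which agrees with the stated total); 10 days of treatment; CRP and LDH on day 1 and at the end; four SpO2 readings a day for 10 days. The documents give no alpha, power, SD, effect size, discharge rate or death rate, so there is no planned figure to reproduce. Every rate and correlation below is an assumption.

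**1. Timing.** Last inhalation on day 10 gives a sample on day 10 + 1 = 11, so the two definitions agree. Suppose a patient stops after day 6. One definition gives day 7, the other day 11, four days apart. The same patient has 6 daily SpO2 medians instead of 10.

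**2. Chance that the gap occurs.** Each patient is 1/10 = 10% of an arm. If each patient independently lacks the day-11 value with probability p, the chance of at least one gap among n patients is 1 − (1 − p)^n.

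- p = 5%: 1 − 0.95^10 = 40% in one arm; 1 − 0.95^30 = 79% in the trial.
- p = 30%: 1 − 0.70^10 = 97% in one arm; over 99.9% in the trial.

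**3. Precision.** Effect detectable with 80% power at two-sided 5% (both assumed):

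| Evaluable per arm | Between two arms | Within one arm (paired) |
|---|---|---|
| 10 | 1.32 SD | 1.00 SD |
| 8 | 1.51 SD | 1.16 SD |
| 7 | 1.63 SD | 1.27 SD |

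**4. Bias if only available pairs are used.** Let improvement have SD 1, with true means of 1.00 (control) and 1.50 (active), and correlation ρ with a standard Normal recovery variable that is shifted by 0.5ρ in the active arm. Patients above an upper threshold leave early; those below a lower threshold die or are transferred. With early discharge only, the mean among those remaining is μ − ρ·φ(c)/Φ(c), where c is the threshold, φ the Normal density and Φ the Normal distribution function.

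Example with ρ = 0.5 and 20% of controls leaving early:

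- Control: c = 0.842, so 1.00 − 0.5 × 0.280/0.800 = 0.83 (rounded).
- Active: c = 0.842 − 0.25 = 0.592, so 1.50 − 0.5 × 0.335/0.723 = 1.27.
- Difference 0.44 instead of 0.50, with 20% and 28% missing.

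This example and other scenarios by simulation:

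| ρ | Controls early | Controls died/transferred | Control mean | Active mean | Difference |
|---|---|---|---|---|---|
| 0 | any | any | 1.00 | 1.50 | 0.50 |
| 0.3 | 10% | 0 | 0.94 | 1.43 | 0.49 |
| 0.5 | 20% | 0 | 0.83 | 1.27 | 0.44 |
| 0.7 | 40% | 0 | 0.55 | 0.90 | 0.35 |
| 0.5 | 0 | 10% | 1.10 | 1.57 | 0.47 |
| 0.5 | 10% | 10% | 1.00 | 1.43 | 0.43 |
| 0.7 | 40% | 10% | 0.70 | 1.00 | 0.30 |

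The two mechanisms push the within-arm mean in opposite directions. With 10% of each, they cancel in the control arm.

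**5. Direction between arms.** In these scenarios the difference shrinks, because treatment is assumed to help. Now let two arms have the same true mean of 1.00 and ρ = 0.5. If only one arm loses its worst 10%, that arm appears better by 1.10 − 1.00 = 0.10 SD. If only one arm loses its best 20% to discharge, it appears worse by 1.00 − 0.83 = 0.17 SD. Direction depends on who leaves, which the documents do not say.

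**The case against.** The strongest reply is that the gap may never arise. No passage says that patients leave before day 11. Every arm has a 10-day course, entry requires substantial lung damage with low saturation or a need for oxygen, and a shorter stay could still end after day 11. Follow-up continues for a month after discharge, so a later sample is not ruled out. The sampling phrase can also be read as the day after the last dose, which would already cover patients who stop early. All this stands, and it is why the point concerns risk and not demonstrated bias. It does not remove the point: no post-discharge measurement is described, and one of two sampling definitions must be chosen.

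A reader might infer several stronger things that the documents do not support:

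- *That the plan prescribes a complete-pair t-test.* It names only a t-test. Dropping incomplete pairs is the likely default when there is one post-baseline value and no missing-data rule, but it is inferred from silence.
- *That SpO2 depends on days 10 and 11.* It uses ten daily medians, so early leavers contribute partial data. The problem is selective loss of the later days.
- *That a patient who can no longer inhale unaided has no blood result.* The requirement "ability to proceed with inhalation by self" is an entry criterion. An inpatient who stops inhaling can still give blood.
- *That the effect would change by a stated percentage.* Suppose CRP falls by 60 mg/L in completers and would have risen by 100 mg/L in one or two of ten patients who die. The mean moves from −60 to −44 or −28, a change of 27% or 53%. The arithmetic is right, but the values are invented, they cover deaths only, and the median stays at −60.

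**Conclusion.** The concern holds as an omission that creates a risk. The end-of-treatment sample has two definitions that can diverge, SpO2 stops when inhalation stops, and nothing says how exits before day 11 are measured or analysed, although a shorter stay is expected. With 10 per arm, one or two such patients matter.

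The size is unknown. Under the assumed correlations of 0.3 to 0.7 and 10% to 40% of controls leaving early, early discharge alone understates mean improvement by 0.06 to 0.45 SD in control and by 0.07 to 0.60 SD in the active arm. With no exits, or exits unrelated to the outcome, there is no bias. The direction is also unknown, because early discharge and death or transfer act against each other. It would be wrong to conclude that the trial's results are biased.

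The documents do not label CRP, LDH or SpO2 as primary. The point is worth correcting, but it is not decisive for the whole trial.

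**What to change.** 1. **Choose one definition of the end-of-treatment sample.** Take it on day 11 for everyone still reachable, including patients who stopped inhaling. Otherwise take it on the day of leaving hospital and record the actual day.
2. **Define the analysis set** as all randomised patients by assigned arm.
3. **Compare each exosome arm with placebo** on change in CRP and LDH by a formal between-arm test, for example a rank test, in place of a within-group t-test plus a box-plot. Analyse SpO2 between arms using all available daily medians.
4. **Report missing values and their reasons by arm.**
5. **Give two sensitivity analyses:** the completers-only t-test, and a worst-rank analysis for death or ventilation. The worst-rank version changes the question being asked, so it should not be the main analysis.

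The cost is SAP wording and one retimed blood sample for early leavers. That retiming may no longer be possible, because Study Design lists enrolment as actual. Exit samples also reflect different exposure times: CRP measured at an early exit has had less time to fall than CRP on day 11, which is why the actual day should be recorded and shown. Items 2 to 5 can be done in any case.

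### CRP and LDH have no tested or interval-estimated comparison with placebo, and for CRP an untransformed t-test would also lose power if the marker is strongly right-skewed

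*Combined protocol and SAP*

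**What the plan says.** The trial randomises 30 patients: "The trial has three groups, each with 10 subjects (n=30"). The blood biochemistry row of the table in Research methods and STATISTICAL CONSIDERATIONS covers "C-reactive protein, LDH", labelled as measures of efficiency and taken at two times: "At the beginning of inhalation (day 1) and on next day of last inhalation (day 11").

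The only test in that row is within group: "The difference in each group between baseline and day 11 will be measured by T-test". Values are summarised as follows: "The data will be presented as a Mean with full range (minmax"). The change is given as a mean "difference with Standard Deviation (SD"). The row mentions no transformation, rank test, standard error or confidence interval, and no comparison with placebo.

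The paragraph below the table applies to all outcomes. It keeps the t-test for change from the start of therapy and describes "comparing data between the main group and the control group using non-parametric method box-plot", where "data are presented in Me - median format with an indication of 25% (q1) and 75% (q3) quartile". The section on Demographics and Baseline Characteristics repeats part of this. No alpha, power, effect size or SD is stated anywhere.

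**The concern.** The trial has a randomised placebo arm, but the one named test for CRP and LDH does not use it. All three arms receive standard therapy, so a fall from day 1 to day 11 within an exosome arm cannot be separated from recovery that placebo patients may also show.

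The planned summaries do not fill the gap. Min-max and SD describe how patients differ from each other. They do not state how precisely the mean change, or its difference from placebo, is known.

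There is a second, conditional issue. If CRP has a long upper tail, a raw mean of 10 values can be dominated by one or two patients. An untransformed t-test then loses power, in a trial that has little to spare.

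**Working it through.** **1. What the text provides for CRP and LDH**

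| Need | Blood biochemistry row | Paragraph below the table |
|---|---|---|
| Test of change within group | t-test | t-test |
| Test against placebo | none | box-plot only, no test named |
| Summary of values | mean, min-max | median, quartiles |
| Confidence interval | none | none |

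The SpO2 row of the same table does name a between-group test and uses medians with quartiles. The omission is therefore specific to the CRP/LDH row. This step needs no distributional assumption and applies to both markers.

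**2. Inputs for the scale question**

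From the documents: 10 per arm, day 1 and day 11, t-test. Assumed: two-sided 0.05, no dropout, lognormal values. CRP-like log-SD is 0.7 to 1.3 and LDH-like log-SD about 0.35. The plan has no power figure to reproduce.

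**3. Between-arm power on day-11 values, unadjusted**

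On the log scale, d = ln(1/ratio)/log-SD and the noncentrality is d × √(10/2) with 18 degrees of freedom.

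- Ratio 0.35: ln(1/0.35) = 1.050, so d = 1.50, 1.05 and 0.81, and the noncentrality is 3.35, 2.35 and 1.81.
- Ratio 0.5: ln 2 = 0.693, so d = 0.99, 0.69 and 0.53.

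The raw t-test and Mann-Whitney figures are simulated. Simulated log-scale power agrees with the formula to within about one point.

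| Ratio | log-SD | Raw t | Mann-Whitney | Log t |
|---|---|---|---|---|
| 0.35 | 0.7 | 78% | 85% | 89% |
| 0.35 | 1.0 | 40% | 55% | 60% |
| 0.35 | 1.3 | 20% | 36% | 40% |
| 0.5 | 0.7 | 45% | – | 55% |
| 0.5 | 1.0 | 20% | – | 31% |
| 0.5 | 1.3 | 10% | – | 20% |

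**4. The planned within-group t-test**

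Take medians of 80 falling to 10, log-SD 1.0 and no correlation between visits. On the log scale d = ln(8)/√2 = 2.079/1.414 = 1.47, and the noncentrality is 1.47 × √10 = 4.65 with 9 degrees of freedom. That gives 98% power, against 78% simulated on the raw scale.

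A 95% t-interval built from the reported mean and SD would have half-width 2.262 × SD/√10 = 0.72 SD. Its simulated coverage of the true mean change is about 90%, 85% and 79% at log-SD 0.7, 1.0 and 1.3. At a log correlation of 0.5 it is about 89%, 84% and 77%.

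**5. LDH-like skew**

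At log-SD 0.35 and ratio 0.75, d = 0.288/0.35 = 0.82. Log-scale power is about 41%, and the raw t-test is about 2 points lower. Coverage of the t-interval is about 94%.

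**6. Baseline-adjusted comparison (ANCOVA)**

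Placebo day-11/day-1 ratio 0.5, active-to-placebo ratio 0.4, log-SD 0.8 to 1.2, log correlation 0.3 to 0.6: power is 20–66% raw and 38–83% on the log scale, a gain of 16 to 25 points. In the LDH-like scenarios (log-SD 0.3 to 0.4, active-to-placebo ratio 0.75) the gain is 2 to 4 points. Between-arm type I error on the raw scale is 3.0–5.0%, so it is not inflated.

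**The case against.** The strongest objection is that the plan is not purely parametric. The paragraph below the table promises medians, quartiles and a non-parametric approach to main versus control. Read generously as Mann-Whitney on day-11 values, that gives 85%, 55% and 36% power at ratio 0.35, within 4 to 5 points of the log-scale t-test. This stands as a limit on the scale argument. It does not supply the missing comparison: no rank test is named, and a rank test alone would give no effect estimate or interval.

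A reader might infer that the plan's intervals are too narrow. The documents do not support this, because the plan states no interval. The under-coverage belongs to a t-interval that someone would build from the reported mean and SD. It is true that SD and n allow such an interval to be built, but for strongly skewed CRP that route is the unreliable one.

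A reader might also infer that LDH suffers as CRP does. The calculation shows otherwise under mild skew.

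Finally, every skewness input is assumed, and use of the raw scale is inferred from silence about transformation. A ratio of 0.35 is a 65% reduction against placebo, which is large; that is why 0.5 is shown as well.

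**Conclusion.** The concern holds in two parts of different strength.

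- **From the text alone, for both markers:** the plan has no tested comparison with placebo and no confidence interval. The table row and the paragraph below it also prescribe conflicting summaries.
- **For CRP only, if it is strongly right-skewed:** the raw scale costs about 10 to 20 points of between-arm power against the log scale over the range shown, and about 20 points for the planned within-group test in the 80-to-10 example. This rests on lognormal values, two-sided 0.05 and complete data on 10 per arm.

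The false-positive rate is not at issue in the between-arm comparison. Nor would the log scale make the trial well powered: with 10 against 10, 80% power needs a standardised difference of about 1.32 on whichever scale is analysed.

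**What to change.** For CRP and LDH separately, compare each exosome arm with placebo by ANCOVA on the log day-11 value, adjusted for the log day-1 value. Report the ratio of geometric means with its 95% CI. Describe each arm by median with quartiles (or geometric mean), which also settles the conflict between the row and the paragraph below it. Keep the within-group change and min-max as description. Replace the box-plot wording with the named test, and keep the plot as a figure.

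The cost is SAP wording only: both measurements are already scheduled, and no patients or visits are added. Effects will read as percentage ratios instead of absolute units. Enrolment is listed as actual, so the change should be dated, and labelled post hoc if unblinded results have already been seen.

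### Time to Clinical Recovery is counted as days in hospital with no rule for in-hospital deaths, so an early death can read as a fast recovery

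*Combined protocol and SAP*

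**What the plan says.** The outcome is specified in one row of the table under Research methods and STATISTICAL CONSIDERATIONS. The row is titled Time to Clinical Recovery. Its method is "Calculation of days in hospital", it is assessed once at the end of the trial, and it is to be presented as a mean with SD. No recovery criteria, start day, end event or rule for deaths is given there or elsewhere.

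The row names no between-arm test. The SpO2 row of the same table does: "The Median by day data (10 measures) will be processed by T-test intragroup and between groups". The general text below the table says "The results will be statistically processed using parametric and non-parametric statistics methods" and, for the comparison with control, "comparing data between the main group and the control group using non-parametric method box-plot". Demographics and Baseline Characteristics repeats this: "comparing data between the main group and the control group using non-parametric method, box-plot". The t-test in the general text is for change from before to after therapy, and a length of stay has no baseline value.

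The Inclusion Criteria require "Pneumonia requiring hospitalization, and oxygen saturation of <94% indoors or a need for auxiliary oxygen", and Eligibility sets no limit on days already spent in hospital. The safety row collects "information about unwanted reactions to inhalation". Study Design lists the enrolment of 30 as actual.

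**The concern.** A shorter hospital stay is one of the benefits listed under EXPECTED RESULTS, and this is the only row that measures it. Days in hospital end in one of two ways, discharge or death, and the row does not separate them. On the literal rule, a patient who dies on day 5 contributes the value 5, the same as a patient who goes home on day 5. If more patients die early in one arm, that arm can appear to recover faster. Leaving deaths out instead breaks the randomised comparison, because the arms then consist of those who survived.

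A reader of the results might not notice, since no row of the table asks for deaths by arm.

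Two further gaps sit in the same row. Stay could be counted from admission, randomisation or first inhalation, and each would comply with the plan. And a box-plot is a display, not a test; its median-and-quartile format also differs from the mean (SD) that the row asks for.

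**Working it through.** The plan states no figure for this outcome, so there is none to reproduce. From the documents: 3 arms of 10, 30 in all. Everything else below is an assumption.

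**Assumed stays.** Lognormal, mean 14 days, log SD 0.4, the same in both arms. SD = 14 × √(exp(0.4²) − 1) = 5.83 days. Standard error of a difference between two arms of 10 = 5.83 × √(2/10) = 2.6 days.

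**How likely deaths are.** At mortality p, the chance of at least one death among 30 is 1 − (1 − p)^30: 45%, 79% and 96% for p = 2%, 5% and 10%. The chance that one exosome arm and placebo have unequal numbers of deaths is 1 minus the sum of squared Binomial(10, p) probabilities: 30%, 54% and 69%. These count imbalance in either direction.

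**Literal reading, deaths in the exosome arm only.** With k deaths on day d, the arm mean falls by k × (14 − d)/10. For d = 5 this is 1 × 9/10 = 0.9 days or 2 × 9/10 = 1.8 days. For d = 20 the mean rises, by 0.6 or 1.2 days. Simulated share of trials in which the exosome mean is below the placebo mean:

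| Day of death | No deaths | One | Two |
|---|---|---|---|
| 5 | 50% | 64% | 77% |
| 10 | 50% | 56% | 62% |
| 20 | 50% | 40% | 31% |

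For day-5 deaths, varying the log SD gives 69% and 84% at 0.3, and 61% and 72% at 0.5. A two-sided 5% pooled t-test (18 df) would wrongly favour exosome in about 2.4%, 4.3% and 7.7% of trials with no, one or two day-5 deaths.

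**Literal reading, random day-5 deaths in both arms.** This removes the one-sided placement.

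| Mortality, exosome vs placebo | t-test favours exosome |
|---|---|
| 2% vs 2%, 5% vs 5%, 10% vs 10% | about 2.4% each |
| 10% vs 5% | 3.4% to 3.5% |
| 20% vs 10% | 5.0% to 5.2% |

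The ranges are differences between simulation runs. In the last two rows the exosome mean is the shorter in about 56% and 63% of trials.

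**Survivors-only reading.** If deaths are unrelated to how long the patient would have stayed, the share stays at 50%. In the extreme case that the one or two longest stayers are those who die, the exosome mean falls to 12.8 or 12.0 days and is the shorter in 68% or 80% of trials.

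**Deaths ranked worst.** With no, one or two deaths in the exosome arm only, exosome ranks better in 49%, 33% and 18% of trials. The measure now moves against the arm with the deaths.

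**Start day.** If days from admission to the start of treatment vary with SD s, independently of later stay, the standard error becomes √((5.83² + s²) × 2/10): 2.6, 2.9 and 3.4 days for s = 1, 3 and 5.

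**The case against.** The strongest objection is to the weight of the figures. The 64% and 77% place every death in one arm, on an early day, and all shifts are below one standard error. With equal mortality, imbalances fall on either side and the t-test keeps its error rate. A reader might infer that the plan as written is tilted towards exosome; it is not. The rule rewards an arm only if that arm truly has more early deaths, or gets them by chance. Late deaths push the other way. This stands, and it limits the claim.

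The row's title also suggests that a patient who died has not recovered, and STATISTICAL CONSIDERATIONS mentions assessment of primary outcomes at discharge. Both make a discharge-based reading plausible. But neither excludes deaths from the count, and the second does not say that this outcome is primary.

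A reader might also infer that deaths would go unreported. That is too strong: the safety row's title covers serious side effects, given as a percentage per group, and follow-up for safety runs to one month after discharge. What is lacking is a commitment to show deaths by arm next to this outcome. The exclusions for expected early death and short life expectancy make deaths less likely without ruling them out.

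Finally, it can be said that the missing start day biases nothing and that descriptive summaries are defensible with 10 per arm in a Phase 1/2 trial. The first is correct: under randomisation, days before treatment add noise, not systematic bias. The second is fair too, which is why these two gaps are secondary.

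**Conclusion.** The concern holds in limited form. The stated rule, applied as written, lets an in-hospital death count as a completed recovery, and no text in the document prevents it. That is a flaw in the outcome's definition, and a better definition is readily available. It should be fixed, but it does not invalidate the trial.

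The omissions are certain from the text; the size of their effect is not. It requires deaths to occur, to differ between arms and to come early. Under the assumed stays and day-5 deaths, the distortion is 0.9 days per death in an arm of 10. If exosome mortality were double placebo's, the chance of a t-test wrongly favouring exosome would rise from about 2.4% to about 3.5% (10% vs 5%) or 5% (20% vs 10%). The documents give no mortality or stay data with which to choose among these cases.

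**What to change.** - Define the outcome as days from randomisation to discharge alive, and name it so. Randomisation is the safer origin, because counting from first inhalation leaves anyone randomised but never treated without a value.
- Give in-hospital deaths a tied worst rank, beyond the longest observed stay.
- State how transfers and withdrawals before discharge are handled.
- Compare each exosome arm with placebo by rank-sum test, with medians and quartiles, and report deaths per arm beside the result. Keep the box-plot as a display.
- Keep mean (SD) as a secondary description of patients discharged alive, labelled as such.
- Enrolment is listed as actual. If the data are already unblinded, label this analysis post hoc and show it beside the planned mean (SD).

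The cost is a wording change, plus a short re-analysis if results are already tabulated. The dates of randomisation, discharge and death should be in the trial and hospital records, so no new measurement is needed. There are three downsides: mean (SD) is no longer the headline; the worst-rank result mixes death with length of stay, which is why deaths per arm must stand beside it; and estimates with 10 per arm will be imprecise.
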